Statistical Analysis Plan

A randomised controlled trial to examine the efficacy of e-cigarettes compared with nicotine replacement therapy, when used within the UK stop smoking service

Version: 1.0
Date: 08.01.2018

Person(s) contributing to the analysis plan	
Name(s) and position(s)	[name] (Co-Investigator) [name] (Chief Investigator) [name] (Study Manager) [name]/[name] (Statistician) [name] (Senior Trial Statistician)
Authorisation	
Position	Chief or principal investigator
Name	[name]
Signature	
Date	11.01.2018
Position	Trial statistician
Name	[name]
Signature	
Date	
Position	Independent statistician
Name	[name]
Signature	
Date	

Introduction

Purpose of statistical analysis plan

The purpose of this document is to provide details of the statistical analyses and presentation of results to be reported within the principal paper(s) of the TEC trial. Subsequent papers of a more exploratory nature (including those involving baseline data only) will not be bound by this strategy but will be expected to follow the broad principles laid down in it. Any exploratory, post hoc or unplanned analyses will be clearly identified in the respective study analysis report.

The structure and content of this document provides sufficient detail to meet the requirements identified by the International Conference on Harmonisation (ICH) and the Barts CTU SOPs.

Members of the writing committee

[name], [name], [name] and [name] were primarily responsible for writing the Statistical Analysis Plan, with input from other members of the Trial Management Group.

The document has been finalised by blinded members of the Trial Management Group and a blinded statistician.

Summary

Background: Electronic cigarettes (EC) have a potential to increase the reach and reduce the costs of the UK Specialist Stop Smoking Service (SSS). Data are needed on their efficacy compared to standard stop smoking medicines, such as nicotine replacement treatment (NRT), which is the most commonly used smoking cessation medicine in the UK.

Design: Randomised controlled trial.

Setting: Four SSS that provide evidence-based treatment to smokers who are typically highly dependent.

Strategy for research and modelling: A straightforward trial comparing EC to no treatment is not ethically acceptable and it will also not clarify the value of EC in the current treatment landscape. Hence, smokers will be randomised to either the usual care arm (UC) that comprises of standard specialist stop-smoking treatment, i.e. behavioural support consisting of 6 weekly support sessions combined with NRT; or to the EC arm that comprises the same behavioural support combined with EC.

Sample: 886 smokers seeking help who are 18 years or older and are not pregnant.

Health technologies being assessed: EC are battery-powered devices that deliver a vaporised liquid nicotine solution in propylene glycol or glycerol. No tobacco, smoke or combustion is involved in their operation and no clinically significant levels of any harmful chemicals have been detected in EC vapour. We provide a starter-kit to participants in the EC arm. We have consulted EC users who advise that the flavour and strength of the refill e-liquid is an important but very personal choice. We will therefore direct participants to select and purchase their own refill e-liquid. This will (a) ensure that people use a refill e-liquid they like; (b) reflect what happens in 'real life'; and (c) avoid giving the EC arm an advantage of free treatment when some participants in the UC arm will have to pay a prescription charge.

Recruitment: Smokers seeking help will be recruited from local SSS and by advertisements in local papers, posters/leaflets and via social media.

Procedure: Prospective participants will attend a screening session and those eligible will provide informed consent, demographic data and details of smoking history, and be randomised on their quit date to one of the two study arms.

Usual Care (UC) arm: Participants will be assisted in selecting NRT of their choice as per usual practice. The NRT will be provided as per standard practice. Participants will attend 6 weekly support sessions and will be contacted by telephone for follow up at 6 and 12 months post quit. Participants reporting abstinence or 50% or more reduction in cigarettes per day at 12 months will be invited for CO validation.

EC arm: Participants will be given an EC starter-kit (18mg/ml nicotine). They will be provided with instructions on how to operate the EC. An information sheet written in collaboration with experienced EC users will also be provided. Participants will be advised on how to obtain further supplies themselves. Support and follow-up contacts will be identical to those in the UC arm.

Measurement of outcomes and costs: The primary outcome measure will be sustained abstinence from 2 weeks post-TQD to one year defined as per Russell validated by CO reading <8 ppm at Week 4 and at one year. Secondary outcomes will include sustained abstinence from 6 months to one year, abstinence at 4-weeks and 6 months, smoking reduction in participants who did not achieve full abstinence, ratings of the treatment, adverse events, and the cost-efficacy of the interventions. An intention to treat analysis will be used with participants lost to follow-up included as non-abstainers.

Sample size: Based on figures from the UK usual care treatment, the 12-month validated abstinence rate associated with UC was initially expected to be 14%. We wished to detect a RR of 1.7 (EC rate = 24%) with 0.95 power, but also have reasonable power (say, 0.75) if the RR should be as low as 1.5 (EC rate = 21%). This latter figure would still represent a clinically significant difference. To achieve these levels of power (2-sided, alpha = 0.05, continuity correction), a total of 886 participants (443 in each group) are required. New national outcome statistics published in 2016, however, show the UC quit rate dropping to 8%. This comprised general practice a pharmacy

services with quit rates of 5% and specialist support with quit rates of 10% for individual and 12% for group support. Using a quit rate of 10% in the UC arm that provides multi-contact support, and 17% in the EC arm (RR=1.70) the study sample size still provides 86% power to detect such a difference with a two-tail test of proportions.

Background

EC are battery-powered devices that provide inhaled doses of nicotine by delivering a vaporised liquid nicotine solution in propylene glycol or glycerol. No tobacco, smoke, or combustion is actually involved in their operation.

EC have largely been marketed as a 'lifestyle' product for smokers who want to reduce the risks of smoking. EC provide levels of nicotine similar to those provided by NRT, but they might have an advantage over existing NRT products because of their ability to provide more realistic sensorimotor and behavioural replacement for smoking.

Current smoking cessation treatments generally provide a combination of behavioural support and evidence-based medicines to target withdrawal discomfort, but sensorimotor factors are not well addressed. EC provide sensations similar to smoking a cigarette by emitting a smoke-like mist or vapour, and provide taste and throat sensations which are closer to smoking than those provided by oral NRT e.g. the nicotine inhalator. There is some evidence that these factors are important for smokers and that their inclusion enhances treatment efficacy [1].

Effects of EC on smoking

At the time of writing there are three published randomised controlled trials examining the effects of EC in helping people stop smoking. One examined their use in people who wanted to quit [2], and two in those who did not [3, 4]

The first trial, which examined the use of EC in people who wanted to quit, compared nicotine-containing electronic cigarettes with 21mg nicotine patches and with non-nicotine electronic cigarettes. At 6-month follow-up there were no significant differences in validated continuous abstinence (7.3% nicotine EC, 5.8% nicotine patch, and 4.1% non-nicotine EC) [2].

The second study examined the effect of EC use (two different doses for 12 weeks) compared to non-nicotine EC in 300 smokers not intending to quit. At one-year follow-up there were no statistically significant differences in 6-month, biochemically verified, abstinence rates (13%, 9%

and 4% in the three groups respectively [3]. Both of these trials used cig-a-like devices that had poor nicotine delivery and are no longer available on the market.

The third RCT examined the use of tank system EC, compared with no intervention in 48 smokers who did not want to quit. At 8-week follow-up, 34% of those given an EC to use had quit smoking compared to none in control group [4].

The first published systematic review, which has recently been updated, showed that EC with nicotine help smokers quit for at least 6 months compared with no nicotine e-cigarettes (RR= 2.29, 95% CI: 1.05-4.96; 9% vs. 4%) [5]. The review gives these findings a 'low' confidence rating using GRADE standards, not because of poor quality studies, but because the systematic review included only two studies.

There is good rationale for why EC could help people stop in that they can deliver nicotine and alleviate urges to smoke. However, more, well-designed, clinical trials are needed to confirm this.

Changes from planned analysis in the protocol

None.

Changes from SAP version 1.0

Not applicable.

Study objectives and endpoints

Study objectives

Primary Objective

To determine the 12-month sustained, biochemically validated abstinence rates in smokers using EC compared to smokers using standard NRT.

Secondary Objectives

1. Abstinence rates between 6 and 12 months.
2. Abstinence rates at 4 weeks and 6 months.
3. Effects of the two treatments on smoking reduction in participants who did not achieve full abstinence.
4. Changes in urges to smoke and other tobacco withdrawal symptoms at 1 and 4 weeks.
5. Ratings of the two treatment approaches by patients.
6. Rates of adverse reactions associated with the use of EC compared to standard NRT.
7. Cost-effectiveness of EC compared to standard NRT.

Outcome measures

Primary outcome measure

The primary outcome measure is carbon monoxide (CO) validated sustained abstinence rates at 52 weeks post target quit date (TQD), defined as per Russell Standard [6].

Secondary outcome measures

The secondary outcome measures are:

1. CO validated sustained abstinence rates between 24 and 52 weeks
2. Sustained abstinence rates at 4 and 24 weeks post TQD (CO validated at 4 weeks)
3. 7-day point prevalence abstinence at 4, 24 and 52 weeks
4. Smoking reduction in participants who did not achieve full abstinence
5. Changes in urges to smoke and other tobacco withdrawal symptoms at 1 and 4 weeks
6. Treatment ratings (e.g. satisfaction, helpfulness)
7. Adverse reactions
8. Cost-efficacy of the interventions.

Abstinence at 4 weeks post TQD is defined as a self-report of no smoking of conventional cigarettes (not a puff) for the previous 2 weeks, validated by a CO reading of <8ppm. Participants who do not provide a CO reading at Week 4 will be considered to be smoking at 4 weeks. 24 and 52 week sustained abstinence will be calculated in accordance with the Russell Standard [6] as a self-report of smoking no more than 5 cigarettes since 2 weeks post TQD, validated by CO readings of <8ppm at the 52 week follow up. Participants lost to follow up or not providing biochemical validation will be included as non-abstainers.

Study methods

Overall study design and plan

Target for randomisation:	886
Date of first randomisation:	11.05.2015
Date of last randomisation:	01.02.2017
Trial design:	Individually randomised, parallel group
Who is blinded:	Participants and researchers are blinded up until the point of randomization.
Randomised Interventions:	Intervention (EC) vs. control (NRT)
Allocation ratio:	1:1

Study population

The study population consisted of people responding to advertising (typically posters, leaflets, digital media, local papers, on local transport, through GP practices, mail outs to previous attendees, and in local radio/newspaper interviews).

Participants were eligible to take part if they were age 18 years and older, a current smoker accessing a stop smoking service (SSS) and able to read/write/understand English.

Participants were excluded from participating if they were pregnant or breastfeeding, had a strong preference to use or not to use NRT or EC in their quit attempt, were enrolled in other interventional research, or currently using NRT or EC.

Method of treatment assignment and randomisation

Randomisation (1:1 in permuted blocks) was undertaken using a web-based application, set up by the Barts Clinical Trials Unit (Barts CTU), and was stratified by study site. Participants who were eligible and consent to take part were randomly allocated to the experimental or control interventions at the target quit day (TQD) session. The TQD was used as the point of randomisation to limit any differential drop-out. The staff randomising the patient accessed the web-based application when the participant was with them, entering their participant ID number, date of birth and initials into the program. There were no stratification factors within study sites. The allocation was immediately provided by the program.

Treatment masking (Blinding)

Participants could not be blinded to the intervention they were receiving and study staff could not be blinded when providing the interventions. However, collective unblinded data were only seen and analysed for the purposes of the DMECs by the trial statistician. The trial statistician was not involved in the decisions about the analysis and the treatment of deviations after randomisation (e.g. protocol violations, losses to follow up, withdrawals from the study).

All other trial staff who have access to outcome data remained blinded until data analysis was complete. Final data analysis will be conducted blind to treatment allocation.

Sample size determination

The 12-month validated abstinence rate (Primary outcome) associated with UC in our setting was initially assumed to be 14% [7]. Our projection of a feasible rate with the EC is based on our work and two published studies. Our work^[8] suggests that EC delivers nicotine quickly, with Tmax occurring within 5 minutes. This is similar to nicotine nasal spray. In a comparative study of the nasal spray + patch versus patch alone in Iceland, 1-year abstinence rates were 27% vs. 11%, Risk Ratio (RR) = 2.45 [9]. More relevant, in a recent cohort study in Italy, a second generation EC achieved 36% CO validated abstinence at 6-months [10]. Assuming 25% relapse between 6 and 12 months [11], this would translate to a 1-year rate of 27%. Relative to our assumed UC rate, this would give RR = 1.9. However, quit rates in countries with little tradition of stop-smoking treatments tend to be much higher than in the UK.

We wish to detect a RR of 1.7 (EC rate = 24%) with 0.95 power, but also have reasonable power (say, 0.75) if the RR should be as low as 1.5 (EC rate = 21%). This latter figure would still represent a clinically significant difference. To achieve these levels of power (2-sided, alpha = 0.05, continuity correction), a total of 886 participants (443 in each group) are required.

Notes: Since the study protocol was written, a new evaluation of the UK stop smoking services was published [12]. The validated one-year quit rate has declined to 8%. This comprised general practice and pharmacy services with quit rates of 5% and specialist support with quit rates of 10% for individual and 12% for group support. The decline is probably due to a 'hardening' of treatment population, e.g. the services see an increasing number of re-attenders, people with serious health issues etc. Using a quit rate of 10% in the UC arm that provides multi-contact support, and 17% in the EC arm (RR=1.70) the study sample size still provides 86% power to detect such a difference with a two-tail test of proportions.

Assuming the true percentage in both arms is 10%, the 95% confidence interval for the difference in proportions will have width of +/-4% around the observed difference.

If the difference in proportions is non-significant, we will undertake a non-inferiority analysis, using a two-sided confidence interval of the difference in the abstinence percentages between the two arms. Assuming that the true percentages are 10% in the control arm and 12% in the intervention arm, our sample size of 886 will provide 88% power to exclude a difference in favour of the standard group of 4% or more.

Data collection

Baseline

The following variables were collected at baseline:

- **Demographics:** includes age, sex, marital status, ethnicity, employment, level of education, eligibility for free prescriptions,
- **Smoking measures:** Fagerstrom Test for Cigarette Dependence (FTCD) [13], previous stop smoking product use, age first started smoking and whether partner/spouse smokes. Mood and Physical Symptoms Scale (MPSS) [14], carbon monoxide reading
- **Current Health and Medications**
- **Health problems checklist**

The following validated questionnaires are also administered at baseline:

- EQ-5D
- Smoking Cessation and Health Service Use Questionnaire

Follow up

The following variables were collected during follow-up visits:

- Current smoking behaviour
- Mood and Physical Symptoms Scale (MPSS) – 1 and 4 weeks post quit only
- Carbon monoxide reading
- Allocated product use, helpfulness, taste and satisfaction ratings (1 and 4 weeks post quit only), purchase and reasons for stopping (where applicable)
- Non-allocated product use and purchase
- Current health and medications
- Health problems checklist

The following validated questionnaires are also administered at 6 and 12 month follow up:

- EQ-5D
- Smoking Cessation and Health Service Use Questionnaire

Timing of data collection

The recruitment period was: 11 May 2015 – 01 February 2017 (22 months) and the study sessions were conducted as follows:

Week -1	Baseline
Week 0:	Randomisation (TQD)
Weeks 1-4:	Treatment sessions, 1, 2, 3 and 4 weeks post TQD (Q+1, Q+2, Q+3 and Q+4)
Month 6:	Follow-up, 24 weeks post TQD (Q+24)
Month 12:	Follow-up, 52 weeks post TQD (Q+52)

Database

Description

Data were entered into the online database, 'Oracle Database 11g', hosted at the Barts Cancer Centre. The Electronic Data Capture forms are web based and built using Java with data validation in JavaScript (Java framework Struts 2).

Data quality

The study team check the data for discrepancies each week, and clarify any potential data entry errors with the relevant advisor/researcher or participant. When recruitment and follow-up are complete, the study team will clean the data in the following way: values for each variable will be sorted, and those at the extremes will be checked to ensure that they are within the expected range.

Source data verification will also be conducted where paper CRFs have been used: a random sample of 10% of CRFs will be selected, and the study team will compare all written entries with those entered onto the main study database. The pre-specified data quality target is $\leq 2\%$ discrepancy rate between entries in the CRF and the electronic database. If an error is found in $>2\%$ of entries, the quality target for data entry will not have been met, and all CRF data will be cross-checked against data in the study database.

Derived and computed variables

All derived and computed variables will be documented in the analysis programmes.

General issues for statistical analysis

General analysis principles

The main analysis for each outcome will use intention-to-treat (ITT) principles, meaning that all participants with a recorded outcome will be included in the analysis, and will be analysed according to the treatment group to which they were randomised. More information on which participants will be included in each analysis is available in the section below. All p-values will be two sided, and the significance level is set at 5%.

Analyses for all outcomes will be presented as:

- The number of participants included in the analysis, by treatment group. NB. for the primary outcome data this will be all randomised participants – see missing data section below);
- A summary measure of the outcome, by treatment group (e.g. mean (SD) for continuous outcomes, number (%) for binary outcomes);
- A treatment effect (risk ratio of abstinence for EC relative to NRT), with a 95% confidence interval;
- A two-sided p-value.

Missing data for outcomes

To deal with incomplete data (i.e. when patients have missing data at one of the follow-up time points) we will:

- Attempt to follow up all randomised patients even if they discontinue participation.
- Include participants lost to follow-up (missing cases) or not providing biochemical validation as non-abstainers.
- Carry out a sensitivity analysis using different assumptions about missing cases (e.g. using the Hedeker method [15] and last known quit status), as well as analyses excluding cases with missing outcomes. NB. Where a participant misses 52 week follow up, but it is already known from their 3, 4 and/or 24 week follow up that they have smoked more than 5 cigarettes since 2 weeks post TQD, they will be counted as smokers for the primary outcome in sensitivity analyses.

Withdrawn participants

Withdrawn participants (i.e. no further follow up permitted) will be included in the analysis as per intention to treat (counted as smokers for the time points after withdrawal, as per Russell Standard).

Participants who died will be excluded from the sample as per the Russell Standard.

Participants who have moved to an untraceable address (documented by returned letters) and whose telephone numbers and email address are no longer in use will be excluded from the sample from the point that notification was received that they were no longer living at the address and their telephone numbers/email address are no longer in use, as per the Russell Standard. They will be included in the sample analysis up until this point.

Analysis of primary outcome

For the primary analysis the proportion of people remaining abstinent at a year will be compared between the study arms using Chi-squared test. The treatment effect will be the risk ratio of abstinence rates for EC relative to NRT. A secondary binomial regression with log link will also be employed, which will allow for a comparison of the two study arms after adjusting for baseline variables identified as significant using a stepwise selection procedure. The analysis will be stratified by the randomization stratification factor, site; this will be done by adjusting the model using a dummy variable for site.

Sensitivity analyses for primary outcome:

A sensitivity analysis will be conducted with only participants who attended at least one treatment session, i.e. who engaged in treatment, included.

Forty two participants received a different EC device due to discontinuation of the original supply. A sensitivity analysis will be conducted with only these participants included.

To deal with participants who switched study products or used the unassigned study product for at least five consecutive days we will include them in the primary analysis in the groups to which they were randomized, but will also conduct a sensitivity analysis where they will be excluded.

Analysis of secondary outcomes

Smoking cessation and reduction outcomes

For the secondary analyses, we will examine the differences between study arms in the proportions of participants with sustained abstinence from 6 to 12 months, and at 4, 24 and 52 week follow-up,

and sustaining a 50% or greater reduction in baseline cigarette consumption and CO levels at 52 weeks, using Chi-squared test/binomial regression.

Sensitivity analyses for secondary outcomes:

Forty two participants received a different EC device due to discontinuation of the original supply. A sensitivity analysis will be conducted with only these participants included.

We will also examine time to relapse in a secondary analysis using a Cox analysis.

Definitions of smoking cessation and reduction outcomes

Primary outcome:

52 week sustained abstinence will be calculated in accordance with the Russell Standard as a self-report of smoking no more than 5 cigarettes since 2 weeks post TQD, validated by a CO reading of <8ppm at the 52 week follow up.

The following rules will apply to the primary outcome:

- Where a participant misses any (or all) of the previous sessions/follow ups, but self-reports smoking no more than 5 cigarettes since 2 weeks post TQD at 52 week follow up, they will be classed as meeting the primary outcome definition providing their self-report is validated by a CO reading of <8ppm at the 52 week follow up.
- Where a participant reports smoking 1-5 cigarettes at more than one session/follow up but reports smoking no more than 5 cigarettes in total since 2 weeks post TQD at 52 week follow up, they will be assumed to have smoked no more than 5 cigarettes in total since 2 weeks post TQD and will meet the primary outcome definition providing their self-report is validated by a CO reading of <8ppm at the 52 week follow-up.
- Where a participant self-reports abstinence at 4 weeks post TQD, but does not give a CO reading at this time point, and at 52 week follow up self-reports smoking no more than 5 cigarettes since 2 weeks post TQD, they will be classed as meeting the primary outcome definition providing their self-report is validated by a CO reading of <8ppm at the 52 week follow-up.

- Where a participant self-reports abstinence at 4 weeks post TQD but fails CO validation at this time point (i.e. they have a CO reading of greater than 8 at 4 weeks post TQD), they will not be included as a CO validated sustained abstainer at 52 week follow up.
- Where a participant reports being 'currently quit' at 52 week follow up, but has not been contactable to provide any other information, they will **not** be counted as a 52 week sustained abstainer, since they will not have been contactable to arrange a CO validation.
- Where a participant reports being 'currently quit' at 4 and/or 24 weeks post TQD and has not been contactable to provide further information at these time points, but then reports smoking no more than 5 cigarettes in total since 2 weeks post TQD at 52 week follow up, they will be assumed to have smoked no more than 5 cigarettes in total since 2 weeks post TQD and will meet the primary outcome definition providing their self-report is validated by a CO reading of <8ppm at the 52 week follow-up.

Secondary outcomes:

- | | |
|---|---|
| 1. CO validated sustained abstinence between 24 and 52 weeks post TQD | 
No more than 5 cigarettes smoked between weeks 24 and 52 accompanied by a CO reading of < 8ppm at week 52.
 
Where a participant reports being 'currently quit' at 52 weeks post TQD, but has not been contactable to provide any other information, they will not be counted as a 24-52 week sustained abstainer, since they will not have been contactable to arrange a CO validation.
 |
| 2. CO validated sustained abstinence at 4-weeks post TQD | 
Not a single puff of a cigarette in the last 2 weeks at 4 week follow up accompanied by a CO reading of < 8ppm at 4 weeks post TQD.
 
Where a participant misses Q+3 but reports not a single puff since their last visit at 4 weeks post TQD, accompanied by a CO reading of < 8ppm at 4 weeks post TQD, they will be counted as a CO validated abstainer at 4 weeks post TQD.
 
Where a participant reports being 'currently quit' at 4 weeks post TQD, but has not been contactable to provide any other information, they will not be counted as a 4 week abstainer since they will not have been contactable to arrange a CO validation.
 |
| 3. Sustained abstinence at 24 weeks post TQD | 
No more than 5 cigarettes smoked since 2 weeks post TQD to 24 weeks post TQD.
 |

Where a participant misses any (or all) of the previous sessions/follow ups, but self-reports smoking no more than 5 cigarettes since their last visit at 24 weeks post TQD, they will be counted as a 24 week sustained abstainer

Where a participant reports smoking 1-5 cigarettes at more than one session/follow up but reports smoking no more than 5 cigarettes in total since their last visit at 24 week follow up, they will be assumed to have smoked less than 5 cigarettes in total since 2 weeks post TQD.

Where a participant reports being 'currently quit' at 24 weeks post TQD, but has not been contactable to provide any other information, they **will** be counted as having smoked no more than 5 cigarettes since their last visit, and included as a 24 week sustained abstainer.

- | | |
|---|--|
| 4. 7-day point prevalence at 4-weeks post TQD | Not a single puff in the last 7-days |
| 5. 7-day point prevalence at 24-weeks post TQD | Not a single puff in the last 7-days |
| 6. 7-day point prevalence at 52-weeks post TQD | Not a single puff in the last 7-days |
| 7. Smoking reduction in participants who did not achieve abstinence at 52-weeks | Self-reported daily cigarette consumption at 52 weeks post TQD reduced by at least 50% of baseline consumption accompanied by a CO reading at 52 weeks reduced by at least 50% compared to baseline. |

NB. Where participants have CO<10 at baseline and report 50% or more cigarette per day reduction at 52 weeks, sensitivity analyses will be carried out including and excluding them.

A sub-analysis of self-reported daily cigarette consumption at 52 weeks reduced by at least 50% of baseline consumption without accompanied CO readings will also be conducted.

Participants with missing data or who report being 'currently quit' at 52 weeks with no further data provided will be classified as non-reducers.

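### The fallback non-inferiority analysis has no stated confidence level, and its 88% power does not fit the 95% level used elsewhere in the SAP, which gives about 81–82%

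*SAP*

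**What the plan says.** The Notes to the SAP's section on Sample size determination provide a fallback. If the abstinence difference is not significant, non-inferiority will be examined "using a two-sided confidence interval of the difference in the abstinence percentages between the two arms". The planning case is "Assuming that the true percentages are 10% in the control arm and 12% in the intervention arm", and the claim is that "our sample size of 886 will provide 88% power to exclude a difference in favour of the standard group of 4% or more". The interval is called two-sided, but its confidence level is not given there or anywhere else in the SAP.

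Three other statements bear on the level:

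- The paragraph just before, in the same Notes, gives the precision of a 95% interval for the same difference in proportions (about 4 points either side).
- General analysis principles states: "All p-values will be two sided, and the significance level is set at 5" (per cent).
- The reporting list in the same section asks for treatment effects with 95% intervals.

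No 90% interval and no one-sided 5% level appears in the SAP.

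**The concern.** A power statement for a non-inferiority analysis means something only with the level of the interval attached. Here the level is missing. The natural reading is 95%, and the printed power does not fit it.

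Two things are at stake. First, non-inferiority is the conclusion planned for the case in which superiority fails, and a reader will judge an inconclusive fallback against the stated power. At 95% the chance of failing to show non-inferiority in the planning case is about 18%, where the text implies 12%. Second, the decision rule is incomplete. A 90% interval carries a nominal one-sided error of 5% against 2.5% for a 95% interval. If the level is still open when the result is known, the choice could decide the conclusion, and the printed 88% could be cited in support of the looser interval.

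**Working it through.** **Inputs**

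- Sample size: "a total of 886 participants (443 in each group) are required" (Sample size determination), allocated 1:1 (Method of treatment assignment and randomisation). So n = 443 per arm.
- True rates: 10% NRT, 12% EC, a difference of +0.02 (Notes).
- Margin: 0.04, from "to exclude a difference in favour of the standard group of 4% or more" (Notes).
- Losses: none to deduct. Under Missing data for outcomes, participants lost to follow-up count as non-abstainers. The few exclusions for death or untraceable address are ignored here, as they appear to be in the SAP.

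**Formula**

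SE = √[p_N(1 − p_N)/n + p_E(1 − p_E)/n] and power = Φ[(margin + true difference)/SE − z].

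SE = √[(0.10 × 0.90 + 0.12 × 0.88)/443] = √(0.1956/443) = 0.02101

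(0.04 + 0.02)/0.02101 = 2.855

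**Reproducing the printed 88%**

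Two-sided 90% interval, z = 1.645: Φ(2.855 − 1.645) = Φ(1.211) = 88.7%.

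**At the level used elsewhere in the SAP**

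Two-sided 95% interval, z = 1.960: Φ(2.855 − 1.960) = Φ(0.895) = 81.5%.

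**Sensitivity to method**

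| Method | 95% interval | 90% interval |
|---|---|---|
| Unpooled normal approximation | 81.5% | 88.7% |
| Pooled SE | 81.4% | 88.7% |
| Constrained maximum-likelihood null variance | 80.6% | 88.2% |
| Exact binomial enumeration, Wald interval | 81.7% | 88.8% |
| Exact binomial enumeration, Newcombe interval | 81.2% | 88.7% |
| Unpooled with continuity correction | 78.5% | 86.5% |

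None of these methods comes near 88% with a 95% interval. For 88% at 95%, the same formula needs 534 per arm (1,068 in total). With 443 per arm, the margin would have to be (1.175 + 1.960) × 0.02101 − 0.02 = 0.046, that is, about 4.6 points.

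**Neighbouring figures in the same Notes**

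- Superiority, 10% v 17%, two-sided 5%: null SE = √(2 × 0.135 × 0.865/443) = 0.02296; alternative SE = √[(0.09 + 0.1411)/443] = 0.02284; power = Φ[(0.07 − 1.960 × 0.02296)/0.02284] = 86.3%. The SAP states 86%.
- 95% half-width with 10% in both arms: 1.960 × √(2 × 0.09/443) = 3.95 points. The SAP states 4.

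Both reproduce at two-sided 5% or 95%. The 88% is the one figure in these Notes that does not.

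**What the choice of level does to the error rate**

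Exact enumeration with true rates on the margin (NRT 10%, EC 6%) gives false non-inferiority in 2.7% of trials with the 95% Wald interval and 5.3% with the 90% interval.

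**The case against.** **The level is unstated, so 88% is not shown to be miscalculated.** This stands. The non-inferiority sentence gives no level, and 88% is about right for a 90% interval. A reader might infer that the SAP prescribes a 95% interval and got its own sum wrong. The text does not go that far: 95% is a strong inference from the neighbouring paragraph and from General analysis principles, but it is not written into the non-inferiority rule.

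**A 90% interval is not the only route to 88%.** This also stands. A test at one-sided 2.5% whose null variance is taken at 10% v 6% has null SE = √[(0.09 + 0.0564)/443] = 0.01818 and power Φ[(0.06 − 1.960 × 0.01818)/0.02101] = 87.7%. However, that test does not correspond to an interval built from the observed rates, which is the analysis described. So it may explain where 88% came from, but it does not give the planned analysis that power.

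**The analysis runs only after a non-significant superiority test, so the power is lower still.** A reader might count this as a further error. By exact enumeration with the 95% Wald interval, the power given non-significance is about 78%. But power is normally quoted unconditionally, and the SAP claims nothing else. A significant result in favour of EC already excludes a 4-point deficit, so the chance of establishing at least non-inferiority remains about 82%.

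**The re-based 10% control rate loses the second power target.** The SAP wished to "have reasonable power (say, 0.75) if the RR should be as low as 1.5". At 10% v 15%, power is about 61% (57.5% with continuity correction). A reader might call this a false claim. It is not: the 0.75 target is tied to an EC rate of 21%, hence to the 14% base, and the Notes never say that it survives at 10%.

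**Nothing in the primary analysis depends on the 88%.** Correct. Overall study design and plan puts the last randomisation at 01.02.2017, and the SAP is dated 08.01.2018, so the sample size was already settled. This lowers the priority, but the decision rule still lacks its level.

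**Conclusion.** The point holds in this form: the non-inferiority interval has no declared level, and the printed power does not fit the level used elsewhere in the SAP. At two-sided 95%, power is about 81–82% against the stated 88%, a shortfall of 6 to 7 points. At two-sided 90% it is 88–89%, but that level is nowhere adopted.

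This rests on 443 per arm, true rates of 10% and 12%, a 4-point absolute margin, and an interval built from the observed rates without continuity correction. With the correction, the 95% figure falls to 78.5%. The superiority power (86.3%) and the stated precision of about 4 points are unaffected. It should be fixed, but it is not critical, because recruitment was complete and the primary analysis does not use the figure.

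**What to change.** Amend the non-inferiority paragraph of the Notes before unblinding, in one of two ways:

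1. **If 95% is meant**, which is the reading consistent with the rest of the SAP: state that non-inferiority is concluded if the lower limit of the two-sided 95% confidence interval for EC minus NRT lies above −4 percentage points, and replace 88% with about 81–82%.
2. **If 90% was meant**: say so, state the one-sided 5% error that it carries, and keep about 88%.

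In either case, name the interval method so that the power and the analysis correspond. For information only, the SAP could add the power given a non-significant superiority test (about 78% at 95%) and the power for a risk ratio of 1.5 at the 10% base (about 61%, or 57.5% with continuity correction). Neither corrects an error.

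The cost is a change of wording. Design, sample size and conduct stay as they are. Under the first option one stated figure becomes less favourable; under the second, the looser error rate is made visible.
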